### 4.3 Descriptive Endpoint(s)

- 1) Evaluation of adverse events
- 2) Evaluation of programmer satisfaction with the Informity tool at the Informity programming visit
- 3) Change in medication usage at 3- and 6-month follow-up visits compared to baseline
- 4) Current (amplitude) at which first transient side effect is noted with each contact configuration tested by the Informity tool
- 5) Current at which first sustained side effect is noted with each contact configuration tested by the Informity tool
- 6) Current at which first partial therapeutic benefit is noted with each contact configuration tested by the Informity tool
- 7) Current at which first complete therapeutic benefit is noted with each contact configuration tested by the Informity tool
- 8) Programmer experience with DBS programming prior to testing Informity tool

## 5.0 SUBJECT SELECTION AND WITHDRAWAL

### 5.1 Subject Population

This clinical study will enroll male and female subjects between the ages of 18 and 80 years who have been diagnosed with PD or ET, and currently have an Infinity DBS system. Subjects must meet all eligibility criteria and provide written informed consent prior to conducting any study-specific procedures not considered standard of care.

### 5.2 Subject Screening and Informed Consent

#### 5.2.1 Subject Screening

Potential patients presenting at the clinical sites will be fully informed about the clinical study, following the established Informed Consent process (described in Section 5.2.2). Once a duly dated and signed Informed Consent form is obtained, the clinical study-specific screening procedures may begin.

The following assessments are performed as part of the screening process:

- Review of patient's medical records
- Review of patient's Infinity DBS system using the Clinician Programmer
- Interview with the patient

## Clinical Investigation Plan

Subjects must be screened for clinical study eligibility by a member of the site's clinical study team (physician and/or research coordinator) previously trained to the CIP, and if applicable will be entered into a site-specific screening log.

In case the subject does not meet all inclusion criteria or meets any of the exclusion criteria, the subject is considered a screening failure. The Principal Investigator or the delegated clinical study personnel will record the screening failure on a screening log as required.

Subject data will be collected following enrollment into the clinical study.

### 5.2.2 Informed Consent

The Investigator or his/her authorized designee will conduct the informed consent process, as required by applicable regulations and the center's IRB. This process will include a verbal discussion with the subject on all aspects of the clinical study that are relevant to the subject's decision to participate, such as details of clinical study procedures, anticipated benefits, and potential risks of clinical study participation. Subjects must be informed about their right to withdraw from the clinical study at any time and for any reason without sanction, penalty or loss of benefits to which the subject is otherwise entitled. Withdrawal from the clinical study will not jeopardize their future medical care or relationship with the investigator.

During the discussion, the Principal Investigator or his/her authorized designee will avoid any improper influence on the subject and will respect subject's legal rights. The subject shall be provided with the Informed Consent form written in a language that is understandable to the subject and has been approved by the center's IRB. The subject shall have adequate time to review, ask questions and consider participation. The Principal Investigator or his/her authorized designee will make efforts to ensure that the subject understands the information provided. If the subject agrees to participate, the Informed Consent form must be signed and dated by the subject and thereafter by the person obtaining the consent prior to any clinical study-specific procedures. The signed original will be filed in the subject's hospital or research charts, and a copy will be provided to the subject.

Failure to obtain informed consent from a subject prior to clinical study enrollment should be reported to Sponsor within 5 working days and to the reviewing center's IRB according to the IRB's reporting requirements.

If, during the clinical study, new information becomes available that can significantly affect a subject's future health and medical care, the Principal Investigator or his/her authorized designee will provide this information to the subject. If relevant, the subject will be asked to confirm their continuing informed consent in writing.

This clinical investigation excludes individuals unable to make the decision to participate in a clinical investigation on their own or who are unable to fully understand all aspects of the investigation that are relevant to the decision to participate, or who could be manipulated or unduly influenced as a result of a compromised position, expectation of benefits or fear of retaliatory response.

In addition, an authorization for use and disclosure of the subject's protected health information, in accordance with the Health Insurance Portability and Accountability Act (HIPAA), must be obtained from the subject or their legally authorized representative.

## Clinical Investigation Plan

### 5.3 Eligibility Criteria

#### 5.3.1 General Eligibility Criteria

Assessment for general eligibility criteria is based on medical records of the site, review of a candidate patient's Infinity DBS system using the Clinician Programmer, and interview with a candidate patient. If some of the clinical tests are not included in site standard tests, they must be done but after written informed consent is obtained. Patients must meet ALL of the inclusion criteria to be considered for the clinical study. If ANY of the exclusion criteria are met, the patient is excluded from the clinical study and cannot be enrolled.

#### 5.3.2 Inclusion Criteria

##### 5.3.2.1 General Inclusion Criteria

###### 5.3.2.1.1 Parkinson's disease patients

1. Patient must provide written informed consent prior to any clinical study related procedure.
2. Patient is 18 to 80 years of age.
3. Patient is diagnosed with Parkinson's disease for at least 4 years according to standard practice.
4. Patient is willing to maintain a constant dose of anti-Parkinson's disease medication indicated as best medical management for at least 1 month prior to study enrollment.
5. Patient is willing and able to comply with the follow-up schedule for the length of the study.
6. Patient has been implanted with an 8-channel directional Infinity deep brain stimulation system in the subthalamic nucleus (STN) within the last 12 months.
7. Patient has had stable deep brain stimulation programming settings for at least 1 month prior to study enrollment.

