The full benefits of dDBS are only realized if the stimulation parameters are selected appropriately to focus the VTA within the targeted brain area and avoid non-targeted brain regions. The Infirmity tool, available within the Clinician Programmer iPad application (Artemis version 3.7 or later), provides a standardized workflow to guide clinicians or trained healthcare providers through the DBS monopolar review screening process. This process involves assessment of the stimulation amplitudes that produce partial or complete therapeutic benefits and transient or sustained side effects, and is performed by individually testing each of the different electrodes on the dDBS lead. The Infirmity tool enables the neurologist to simultaneously perform this testing on a patient and record the results (Figure 3). Moreover, the tool allows the neurologist to review the results in different formats to aid in the selection of the best contact configuration for that patient (Figure 4). The selection of the best contact configuration is made on the basis of maximizing the width of the therapeutic window and minimizing stimulation power (total electrical energy delivered [TEED]).

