## Clinical Investigation Plan

### 4.2 Secondary Endpoints

- 1) Change in UPDRS III for PD subjects or Fahn-Tolosa-Marin tremor rating scale for ET subjects at 3- and 6-month follow-up visits compared to baseline
- 2) Change in quality of life measurement as measured by the PDQ-39 for PD subjects or QUEST for ET subjects at the 3- and 6-month follow-up visits compared to baseline
- 3) Duration of programming at the Informity programming visit compared to the most recent programming session prior to enrollment
- 4) Change in TEED at the 3- and 6-month follow-up visits compared to baseline

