#### 5.3.3 Exclusion Criteria

##### 5.3.3.1 General Exclusion Criteria

1. Individuals unable to make the decision to participate in a clinical investigation on their own.
2. Patient is currently programmed with segmented electrodes, and cannot tolerate omnidirectional programming.
3. Patient is being evaluated for a lead revision.

*This confidential document is the property of Abbott and shall not be reproduced, distributed, disclosed or used without the express written consent of Abbott*

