## Clinical Investigation Plan

### 6.0 TREATMENT AND EVALUATION OF ENDPOINTS

#### 6.1 Baseline

##### 6.1.1 Baseline Assessments

Subjects should have omnidirectional stimulation in use at the time of the Baseline visit. Informity should not be used. The following assessments and information will be collected at the Baseline visit:

- Demographics- subject's age and gender
- Disease history- subject's year of PD or ET symptom onset, year of initial PD or ET diagnosis, subject's impression of worst symptom (PD subjects only)
- Baseline programming- subject's current DBS programming parameters
- Therapeutic window of current parameter set
- TEED of current parameter set
- Duration of the most recent programming session preceding enrollment from the Clinician Programmer session logs (if available)
- Medication dosage (only PD or ET medications)- indicate the drug category the subject is currently taking on a long term basis, i.e. no short term medication
- Preoperative motor symptom evaluation (medication ON) from medical records (if available)
- Preoperative quality of life assessment from medical records (if available)
- DBS implant information
- Pre-op MRI and post-op CT images

An encrypted thumb drive containing de-identified MRI and CT images for all study subjects will be provided to sites and images will be sent to the Sponsor.

The following activities will be performed at the Baseline visit:

- Quality of life assessment
- Motor symptom evaluation (stimulation ON/medication ON) performed by a blinded assessor

The quality of life assessment must be performed prior to the motor symptom evaluation. Quality of life assessments will be performed using PDQ-39 for PD subjects, and QUEST for ET subjects (see Section 6.3.2). Quality of life assessment does not need to be collected if a patient was reprogrammed to omnidirectional stimulation on the same day as the Baseline visit. Motor symptom evaluation will be performed using UPDRS part III for PD subjects and Fahn-Tolosa-Marin tremor rating scale for ET subjects. For both evaluations, responses are rated on a 0 to 4-point scale where 0 indicates 'none' and 4 indicates 'severe' symptom. Motor symptom evaluation will be performed by a blinded assessor, who will not be aware of the subject's programming.

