### 8.1 Statistical Analyses

#### 8.1.1 Primary Effectiveness Endpoint Analyses

The hypotheses for the primary endpoints are that the Informity tool will identify DBS parameters that:

1. Have a larger therapeutic window size compared to programmed parameters at baseline
2. Have a lower TEED compared to programmed parameters at baseline

A comparison of therapeutic window and TEED will be performed for the contact configuration used at baseline, and the contact configuration used after Informity programming with the Informity tool, using a paired t-test. All statistical analyses will be conducted assuming a type-1 error rate of 0.05 unless specifically stated otherwise. The change in TEED from baseline to Informity programming will be used to calculate a corresponding battery longevity projection.

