### 15.5 Steps Taken to Control or Mitigate Risks

The devices used in this study are FDA-approved devices in commercial distribution. In-depth recommendations, special precautions and instructions regarding use of the Informity tool are included in the IFU.

It is also stated in the IFU that the devices can only be used by physicians who have received appropriate training on how to use the device. This statement is interpreted to mean that the physician users are expected to be aware of the known and foreseeable safety risks associated with the use of the devices.

Risks associated with the use of the device under investigation are minimized through device design, investigator selection and training, pre-specified patient eligibility requirements, and study monitoring to ensure adherence to the protocol. Stopping rules will be applied for subject safety through enrollment. All adverse events will be reported to the Sponsor and will be monitored internally for safety surveillance purposes.

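### The plan neither bars nor records earlier use of the Informity tool, which exposes the programming-duration comparison and, less clearly, the baseline measurement

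*Combined protocol and SAP*

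**What the plan says.** **Entry.** Item 7 for Parkinson's disease (5.3.2.1.1), repeated for essential tremor in 5.3.2.1.2 and in Appendix IX, reads "Patient has had stable deep brain stimulation programming settings for at least 1 month prior to study enrollment". Item 6 sets the time since implant: "Patient has been implanted with an 8-channel directional Infinity deep brain stimulation system in the subthalamic nucleus (STN) within the last 12 months". The essential tremor criterion is the same for the Vim target. The only exclusion about programming (5.3.3.1, item 2) is "Patient is currently programmed with segmented electrodes, and cannot tolerate omnidirectional programming".

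**Availability of the tool.** Section 1.1.1 states: "The Infirmity tool, available within the Clinician Programmer iPad application (Artemis version 3.7 or later), provides a standardized workflow" (spelling as printed). Section 2.2.1 lists that app as market released, and 15.5 adds: "The devices used in this study are FDA-approved devices in commercial distribution".

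**Baseline.** Sections 5.4 and 6.1.1 call for omnidirectional stimulation from enrollment through the Baseline visit. Section 6.1.1 then adds "Informity should not be used". Its list of Baseline items includes the current parameters and, if available, the length of the last pre-enrollment session from the programmer logs. It does not include how the settings were chosen.

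**Bias control.** Sections 3.2 and 6.2.1 require that the Informity programmer be a different person from whoever programmed the subject before.

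**Comparisons.** The first primary hypothesis (8.1.1) is that parameters identified by the tool "Have a larger therapeutic window size compared to programmed parameters at baseline". The second is the same for lower TEED. Secondary endpoint 3 (4.2) is "Duration of programming at the Informity programming visit compared to the most recent programming session prior to enrollment", and 8.1.2 hypothesizes that the Informity session is the shorter one.

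**The concern.** A before-and-after comparison says something about a tool only if the before measurement was obtained without it. Here the tool sits in a commercial app, subjects may have been implanted up to 12 months before entry, and nothing at entry asks whether the tool has already been used on them. If it has, two things are at risk.

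- **Duration.** The pair in secondary endpoint 3 may be one Informity session against another. Such a pair says nothing about whether the tool saves time.
- **Therapeutic window and TEED.** The baseline may already carry part of the tool's choice. Alternatively, a subject may be taken off a setting that the tool had found and then be credited with finding it again.

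Prior use is not a listed data item, so the analyst has no planned way to tell which subjects are affected.

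**Working it through.** The plan states no power, effect size or standard deviation, so there is no figure of its own to reproduce. The check is mainly a reading of the rules against each kind of prior user.

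**Step 1: do the entry criteria address prior use?** No. All inclusion and exclusion items in 5.3 and Appendix IX were read, and none mentions the tool. Stability for one month concerns how long settings were held, not how they were found. The different-programmer rule restricts the person, not the method.

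**Step 2: which cases do the Baseline rules catch?**

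| Prior use | Rule that might apply | Result |
|---|---|---|
| Informity-chosen directional setting still in use at Baseline | Omnidirectional rule (5.4, 6.1.1) | Should not occur |
| Informity-chosen omnidirectional setting, or ring mode at a level found with the tool | The no-Informity sentence in 6.1.1 | Barred only if that sentence covers how the settings were originally chosen |
| Entered on Informity-chosen segments, then reverted to omnidirectional mode | Exclusion item 2 | Eligible if omnidirectional mode is tolerated; any regained benefit counts as new |
| Last pre-enrollment session was an Informity session | None | Allowed as the duration comparator |

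In row 1, the rule is worded as something that should be done. The subgroup in 8.3 also allows for individual segments as cathode at Baseline. Those sections need to be reconciled.

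In row 2, the procedure in 6.2.1 first finds the best segmented level. Returning to ring mode at that level would therefore keep the tool's choice of level.

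**Step 3: what could this do to the primary endpoints?** Let p be the fraction of prior users, D the mean change in tool-naive subjects and E the mean change in prior users. Then

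observed mean change = (1 − p) × D + p × E.

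- If E = 0, the result is (1 − p) × D. For p = 0.10, 0.25 and 0.40 the factor is 0.90, 0.75 and 0.60.
- If E = D, nothing is lost.
- If E exceeds D, for example through regained benefit in reverted subjects, the change is overstated.

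The documents give neither p nor E. The factor (1 − p) is thus the worst-case dilution for E no worse than zero, not an expected value.

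**Step 4: illustration of the worst case for power.** Assumptions: paired t-test, two-sided 0.05 (the plan does not state sidedness), standardized effect d set to give 80% power without prior users, and E = 0. The diluted effect is (1 − p)d / √(1 + p(1 − p)d²). For n = 40, d = 0.454 and p = 0.25 this is 0.3405 / √1.0386 = 0.334.

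| p | Power, n = 40 (d = 0.454) | Power, n = 20 (d = 0.660) |
|---|---|---|
| 0 | 80% | 80% |
| 0.10 | 70.5% | 69.6% |
| 0.25 | 54.1% | 52.5% |
| 0.50 | 27.6% | 26.5% |

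These figures describe an assumed scenario, not this study.

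**The case against.** The best defense is that the Baseline rules already do most of the work. Directional settings should be gone by Baseline. The no-Informity sentence directly follows the one on which stimulation should be in use, so it can fairly be read as describing the baseline settings themselves. At the Informity visit the three single segments at the best level must be tested (6.2.1), so even a subject with a tool-chosen omnidirectional baseline can move to a new configuration. The objective is to characterize performance, and the hypotheses compare with whatever was programmed at baseline, not with a defined conventional method. Appendix VIII records that version D deliberately allowed previous directional stimulation. The documents do not say when app version 3.7 appeared or how often the tool was used in routine care. The case report forms are held separately and might contain a field for prior use.

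Most of this stands, and it limits the point. A reader might infer that the baseline is in general an Informity result and that the primary estimates are diluted by (1 − p). The documents do not support that: the omnidirectional rule stands against the first part, and the required segment testing and the reverted subjects stand against assuming zero change. Nor do the documents show that prior users can never be identified, only that no listed item does so.

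The defense does not reach the duration endpoint. Its comparator is fixed before enrollment, where no Baseline instruction clearly applies. Nor does it remove the ambiguity of the no-Informity sentence, which has no look-back and is not an eligibility rule.

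**Conclusion.** The point holds in a limited form. The plan is silent, in its criteria and its listed Baseline items, on whether the tool was used before the study. For secondary endpoint 3 the gap is plain: as written, an Informity session can serve as the comparator for an Informity session. For therapeutic window and TEED the exposure is narrower. It is confined to omnidirectional settings or levels found earlier with the tool, and to subjects reverted from tool-chosen segments. The first group would tend to pull the change toward zero, while the second could add regained benefit. The net size and direction are therefore unknown. The 90%, 75% and 60% factors rest on zero expected change in prior users and on assumed values of p. With at most 20 subjects per diagnosis a few prior users could matter, but the documents do not show that there are any.

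**What to change.** 1. **Future enrollees.** State in 5.3.3.1, Appendix IX and 6.1.1 that neither the baseline settings nor the comparator session may have been established with Informity. This also settles the meaning of the sentence in 6.1.1.
2. **Recording.** Add prior tool use (yes, no, unknown) to the Baseline items. Take it from medical records, which screening already reviews (5.2.1), and from session logs where they show it. The plan cites those logs only for duration, so the unknown category is needed.
3. **Duration test.** For subjects already enrolled, omit comparator sessions known to be Informity sessions. Section 8.5 already leaves out subjects whose log is missing or corrupted, so this is one more sentence there.
4. **Primary endpoints.** Keep the planned analysis in all subjects and prespecify a sensitivity analysis of therapeutic window and TEED in subjects recorded as tool-naive. Replacing the primary population after enrollment has begun is not recommended, because it would change the planned analysis and shrink a study of up to 40.

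**Cost:** one exclusion line, one form field and two analysis sentences. Enrollment may be slightly slower, and the duration comparison may lose a few subjects.

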###### 5.3.2.1.2 Essential tremor patients

1. Patient must provide written informed consent prior to any clinical study related procedure.
2. Patient is 18 to 80 years of age.
3. Patient is diagnosed with essential tremor for at least 4 years according to standard practice.
4. Patient is willing to maintain a constant dose of anti-tremor medication indicated as best medical management for at least 1 month prior to study enrollment.
5. Patient is willing and able to comply with the follow-up schedule for the length of the study.
6. Patient has been implanted with an 8-channel directional Infinity deep brain stimulation system in the ventral intermediate (Vim) thalamus within the last 12 months.
7. Patient has had stable deep brain stimulation programming settings for at least 1 month prior to study enrollment.

